Rationale: Substance use problems (misuse and addiction) are common among patients with Severe Mental Illness (SMI). Substance use problems are often not recognized and therefore not incorporated in the treatment for patients with SMI which leads to more admissions, behavioural problems, aggregation of psychiatric and addiction problems and poorer treatment outcome. Therefore, early detection by screening and assessment is important but this is often omitted in psychiatric departments because there is no suitable instrument (short but informative). NIDA (National Institute on Drug and Addiction) developed the TAPS (Tobacco, Alcohol, Prescription medication and other Substances)-tool for this purpose.

Objective: The aim of the study is to investigate the reliability and validity of the Dutch version of the TAPS-tool. This will be investigated in 2 groups: patients without intellectual disabilities treated in FACT (Flexible Assertive Community Treatment) teams and patients with intellectual disabilities. For the latter group, an adjusted version of the TAPS-tool will be developed. For both groups the TAPS outcome will be compared to a golden standard.

Study design: observational study

Study population: adult people with SMI, with or without intellectual disabilities.

Main study parameters/endpoints: We investigate the suitability of the TAPS-tool to detect substance use problems in a quick and accurate way and evaluate the validity.

Nature and extent of the burden and risks associated with participation, benefit and group relatedness: The burden of this research are additional questions about addictive behaviour (about 15 – 20 minutes) by patients who get several tests and questionnaires for their standard treatment. There are no risks associated with participation. By having a suitable instrument to detect substance use problems, these problems will be detected more in clinical practice. This leads to a better treatment.

1. INTRODUCTION AND RATIONALE

20 to 60% of patients treated within mental health care have dual diagnosis problems; a combination and interaction of a psychiatric disorder and substance use. The more severe the psychiatric condition, the higher the risk of comorbid addiction problems. A mild intellectual disability (LVB) also increases the risk of addiction problems (triple problem). Within the target group of patients with severe psychiatric disorders, a significant proportion appears to function at the level of a mild intellectual disability (Seelen-de Lang et al., 2019). Both serious psychiatric disorders and addiction problems lead to social problems, high social (care) costs, poorer treatment results and a poorer prognosis.

Addiction problems are often overlooked in patients with a serious psychiatric disorder, whether or not in combination with MID (Ananth, 1990; Shaner, 1993; Nagel, 2018). Incomplete and/or inadequate diagnosis can lead to incomplete and/or inadequate treatment, which leads to poorer treatment outcomes such as increased risk of relapse, (re)admissions, homelessness, violence, somatic disorders, and higher psychological burden and economic costs (Drake, 1998; Caton, 1994; Lindqvist & Allebeck, 1989; Bartels, 1993; Safer, 1987; Shaner, 1995).

The NIDA (National Institute for Drugs and Addiction, USA) developed the TAPS questionnaire in 2016 that provides a screener to address these issues (McNeely et al., 2016; Gryczynski et al., 2017). Including screening for drug addiction in the TAPS is of added value for the GGZ target group. A Dutch translation is now available in collaboration with the NIDA (DeJong et al., 2019). However, due to the complicated language, this translation is unsuitable for patients with MID. The NIDA has also not developed a version for this target group. By implementing the TAPS as a standard screener within mental health care, more insight can be gained into problematic alcohol and substance use, so that treatment can be adapted accordingly. However, it is important that the validity of the Dutch version is still being established.

The SumID-Q, a structured interview used to investigate addiction problems in patients with MID, has a duration of 45-60 minutes. Because of this time investment, the instrument is only used if there is already a suspicion of highly problematic substance use. As a result, not everyone is screened, which leads to underdiagnosis and undertreatment. We want to be able to trace precisely the group of patients who are not immediately suspected of use, but who may do so anyway, in order to optimize the treatment. In addition, the SumID-Q only asks about alcohol, tobacco, cannabis and “other drugs”. Incorrect medication use is not included. The addition of this extra category, together with a greatly shortened administration time of the TAPS-LVB, ensures that the group of triple problem patients can be better mapped.

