3. STUDY DESIGN

This is a descriptive study based on routinely collected data. The FACT teams that participate in the study work according to a care program in which screening and assessment are part of the standard care. This implies that since 2016, screening has been carried out at the start of treatment for: PTSD, a mild intellectual disability, addiction problems. The current screening for addiction problems is too limited and lacks a follow-up step in the form of structured assessment. In addition, at the start of treatment and annually in preparation of the treatment plan, the level of complaints is assessed by the care provider involved and the phase of recovery and the patient's quality of life are assessed. We want to use this data from patients in whom there is no suspicion of mild intellectual disability in anonymised form. In the research into the validity of the TAPS, we want to measure whether there is a relationship between the existence of problem substance use and a poorer treatment outcome (less decrease in complaints), and a reduced quality of life.

The TAPS has already been included as a replacement for the previously used screener for addiction problems by the various substantive advisory bodies that deal with the content and improvement of the care of the GGZ Oost Brabant.

In order to investigate the concurrent validity of the TAPS, a group of at least 40 patients will be asked permission to administer some parts of the MATE in addition to the TAPS.

The TAPS is too difficult for patients with intellectual disabilities. We therefore made adjustments to the translated TAPS (see below). The adjusted version for patients with ID is called the TAPS-ID. The validity of the TAPS-ID is examined by the comparison of the TAPS-ID and the SumID-Q (an instrument specially developed to map addiction problems in patients with MID). This will be carried out in a special department within secondary healthcare for patients with a combination of a severe mental disorder and intellectual disability (LVB-P) and in a healthcare setting for people with intellectual disabilities with minimal or light mental disorders (ORO). The SumID-Q is part of standard care for both departments. Trained employees who administer the SumID-Q also take the TAPS-ID.

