Participants were invited by telephone for the regular appointment that was scheduled at least one day later. During this telephone conversation, information was given about the validation study of the TAPS and patients were asked if they want to think about voluntarily participation. During the appointment, the information about the validation study was reviewed again, any additional questions from the patients were answered and when the patient agreed for participation, informed consent was signed. Patients signed informed consent to use the answers of the TAPS and MATE and background information (age, gender, diagnosis, medication, level of education) anonymously for this scientific purpose.

To investigate research objective 1, the following measuring instruments are used:

TAPS:

Tobacco, Alcohol, Prescription medication and other Substances-tool.

The TAPS-tool is a 2-phase screening instrument to detect substance use problems which can be used as an interview or as a self-administered questionnaire. According to McNeely et al., the diagnostic characteristics of both ways are similar (McNeely et al., 2016).

The TAPS-1 (screener) pretends to detect unhealthy substance use in the past year quickly and is based on NIDA's quickscreen. It contains of four multiple choice questions where the patient answers how often they used tobacco, alcohol, other drugs, and prescription medication in te past year on a five point Likert-scale.

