good test-retest reliability: substance risk scores from two administrations within 1-4 weeks has excellent concordance (90–98%) and a high correlation (ICC 0.90–0.97) for tobacco, alcohol, and drugs (McNeely et al., 2014). The ASSIST-Lite (a shortened version of the ASSIST) has a single factor structure on which all substances loaded (eigenvalue range, 2.42–3.81). It also has a consistent pattern of positive loadings on this factor (all ≥ 0.303) (Ali et al., 2013). For the TAPS-2, only ADHD medication and questions about the failure to reduce or stop the use of marihuana, amphetamines and anxiolytics have been added to the ASSIST-Lite. There are nine categories on the TAPS-2: tobacco, alcohol, marihuana, stimulant drugs, opiates, anxiolytic medication, ADHD medication and 'other substances'. Only the elements with a positive score on the TAPS-1 are further assessed. For every category, the assessment with the TAPS-2 contains the usage for the last 3 months and two or three additional questions which can detect unhealthy use. For scoring both the use for the last 3 months and an affirmative answer on each of the additional questions lead to one point. A total score is calculated for each of the categories separately by adding the positive answers together. A total score of +2 per category induces a risk of a substance use disorder and indicates more assessment. Investigation of the TAPS-2 has been done by a comparison with the Composite International Diagnostic Interview (CIDI). Problematic use (with a cut off score of +1) for tobacco has a sensitivity of 0.93 and specificity of 0.87. Alcohol has a sensitivity of 0.74 and specificity of 0.79. For problematic use of illicit and prescription drugs, sensitivity ranges from 0.82 for marijuana to 0.63 for sedatives, and specificity is 0.93 or higher. For identifying any SUD, sensitivity was lower, but a cut off score of +2 greatly increases the likelihood of having a SUD as measured by the CIDI (McNeely et al., 2016).

HoNOS:

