- 2) A score of 8 or 9 out of 9 questions about dependency / misuse, or
- 3) A total score of 12 or more (range 0-20) on questions about desire

Objective 2:

SumID-Q is part of standard care for both departments (LVB-P and ORO). For the purpose of the validation of the TAPS-ID, patients are asked if they are voluntary willing to participate on the study by adding the TAPS-ID to the SumID-Q. Second, after completing the TAPS-ID and the SumID-Q, but before the scoring it, the assessor also rated the severity of the substance use problems on a five-point Likert scale by answering the following question: "I rate the addiction problem of the client as...". Possible answers were: absent, mild, moderate, severe, very severe.

Psychologists or psychiatric nurses are the assessors. They invite the patient for an appointment to take the SumID-Q. Participants were invited by telephone for the regular appointment that was scheduled at least one day later. During this telephone conversation, information was given about the validation study of the TAPS and patients were asked if they want to think about voluntarily participation. During the appointment, the information about the validation study was reviewed again, any additional questions from the patients were answered and when the patient agreed for participation, informed consent was signed. Patients signed informed consent to use the answers of the TAPS-ID and SumID-Q and background information (age, gender, diagnosis, medication) anonymously for this scientific purpose.

The answers from the TAPS-ID and SumID-Q are recorded on paper. Papers are stored in a locked closet at the department of care (GGZ or ORO).

To investigate research objective 2, the following measuring instruments are used:

SumID-Q:

The SumID-Q maps out what the client knows about psychoactive substances, what he/she knows, thinks about them, what is used in his/her environment, what he/she

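### The TAPS-ID medication items have no criterion reference under Objective 2, because the SumID-Q omits medication misuse, and the plan does not exempt them from the comparison

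*Combined protocol and SAP*

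**What the plan says.** Section 1 of the combined protocol and SAP describes the reference instrument's content: "the SumID-Q only asks about alcohol, tobacco, cannabis and" other drugs. It adds that "Incorrect medication use is not included". The next sentence makes this gap one of two advantages of the new tool: "The addition of this extra category, together with a greatly shortened administration time of the TAPS-LVB" is expected to map these patients better. LVB is the document's abbreviation for mild intellectual disability ("A mild intellectual disability (LVB) also increases the risk of addiction problems"), and section 3 calls the adapted tool TAPS-ID.

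Section 3 then sets the validity design: "The validity of the TAPS-ID is examined by the comparison of the TAPS-ID and the SumID-Q". The Statistical Analysis section names the SumID-Q as golden standard for this group. Under Research goal 2 it plans internal consistency and one correlation between the TAPS outcome and the SumID-Q outcome. Section 6.6 plans sensitivity, specificity and AUC for single items or sets of items, without tying this to one objective.

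Section 5.3 shows the medication content of the parent tool. TAPS-1 asks "how often they used tobacco, alcohol, other drugs, and prescription medication", and the TAPS-2 categories include "marihuana, stimulant drugs, opiates, anxiolytic medication, ADHD medication and" other substances. Each TAPS-2 category has its own total.

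**The concern.** A reference standard can only test the content that it measures. Here the protocol states that its reference lacks a domain, promotes that domain as a strength of the index test, and then plans accuracy for the index test's items with no rule for the unmatched ones.

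Two things are at stake. First, accuracy figures for the medication items would have no meaning, because a SumID-Q result says nothing about whether medication is misused. Second, a favourable SumID-Q result could be reported as validating the TAPS-ID as a whole, including a category never tested against a criterion. Objective 2 is to validate and implement the tool, so that conclusion would carry into practice.

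**Working it through.** The documents give no figure for this point, so the check sets index content against reference content.

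**Domain by domain** (TAPS content from section 5.3, SumID-Q content from section 1):

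| Parent TAPS content | SumID-Q counterpart |
|---|---|
| Tobacco | Tobacco |
| Alcohol | Alcohol |
| Marihuana | Cannabis |
| Stimulant drugs | Other drugs |
| Opiates | Other drugs, if illicit; unclear if prescribed |
| Other substances | Other drugs, if illicit; unclear if medicines |
| Prescription medication (TAPS-1); anxiolytic and ADHD medication (TAPS-2) | None |

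**Are medication items in the TAPS-ID?** Its item list is not given, and the final version follows piloting. Section 5.3 describes added pictures, split questions and simpler words; it removes no category. Section 1 counts the category as a benefit. Retention is the natural reading, but it is inferred.

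**Is there another reference in Objective 2?** Section 5.3 says that "after completing the TAPS-ID and the SumID-Q, but before the scoring it, the assessor also rated the severity of the substance use problems". This is one global rating, made with knowledge of the TAPS-ID answers, and the statistical text gives it no role. Recorded medication is background information, not a measure of misuse. By contrast, the MATE in Objective 1 does ask about use of sedative medicines.

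**Consequence by type of score:**

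1. *Per category or per item.* Shared domains are compared with their counterparts and are unaffected. Medication items have no reference value, so their sensitivity, specificity and AUC cannot be estimated, whether the group reaches the required 40 patients or the ceiling of 100.
2. *Pooled score.* The correlation mixes matched and unmatched content. It could rise or fall, depending on how medication misuse relates to the SumID-Q outcome, and the documents give nothing on that.
3. *Any-positive score, if a SumID-Q cut-off is set.* Adding medication items can only add positives, so apparent specificity stays the same or falls. Let Sp be specificity on shared domains, m the share of SumID-Q negatives with medication-only misuse, and s the TAPS-ID sensitivity for it. If such misuse is independent of false positives on shared domains, apparent specificity = Sp × (1 − m × s).

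An illustration of item 3, with inputs assumed: m = 0.05 to 0.20; s = 0.63 to 0.89, borrowed from the sedative (TAPS-2) and prescription-misuse (TAPS-1) sensitivities in section 5.3; Sp = 0.85 or 0.93.

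- Sp = 0.85: 0.85 × (1 − 0.05 × 0.63) = 0.823, down to 0.85 × (1 − 0.20 × 0.89) = 0.699.
- Sp = 0.93: 0.93 × (1 − 0.05 × 0.63) = 0.901, down to 0.93 × (1 − 0.20 × 0.89) = 0.764.

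This shows the mechanism only. It is not an estimate for this study, and the conclusion does not depend on it.

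**The case against.** The best defence has four parts.

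- *Scoring is per category.* Section 5.3 totals each TAPS-2 category separately and states no change for the TAPS-ID. This stands: distortion of an overall result needs a pooled or any-positive score, which the text for Objective 2 does not specify. A sentence in section 6.6 about a total TAPS score concerns Objective 1 and breaks off, so it settles nothing here.
- *Goal 2 plans only convergent validity.* Its one planned comparison is a correlation, which does not need identical content, and ROC analysis appears under goal 1 only. This narrows the point. It does not remove it, because the same section calls the SumID-Q a golden standard and section 6.6 plans accuracy without limiting it to Objective 1.
- *The gap is disclosed.* Section 1 states it openly and does not promise separate validation of the medication category. That is fair, but the disclosure never reaches the analysis text.
- *Part of the remedy is there.* Section 6.7 already plans descriptive statistics by substance, and section 6.6 leaves room for a shared-domain combination. What is missing is a rule that fixes the choice and states the limit.

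A reader might infer that the SumID-Q comparison is invalid as a whole, or that the planned correlation will be too low. The documents support neither. The shared domains have a reference, and the direction of any shift in a correlation is unknown.

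**Conclusion.** The point holds and should be fixed before analysis. The plan names a reference that by its own account does not cover medication misuse, and it does not exempt the medication items from accuracy analysis against that reference. Criterion validity of the medication category in patients with intellectual disability cannot be established by this study, whatever the sample size. Internal consistency can still be assessed.

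The gap is confined to the medication items and to any overall score that includes them. The size of the effect on such a score cannot be derived from the documents.

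The content mismatch rests on the protocol's own statement and is firm. Its effect on the analysis assumes that the TAPS-ID keeps its medication items, and the supplied text gives neither the final item list nor a SumID-Q score or cut-off.

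**What to change.** Under Statistical Analysis (Research goal 2) and in section 6.6:

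1. Limit the TAPS-ID versus SumID-Q comparison to shared domains: tobacco, alcohol, cannabis, and illicit drugs mapped to the SumID-Q other-drugs category.
2. Set the mapping and the SumID-Q outcome for each domain beforehand, as far as the SumID-Q allows. Work from the final TAPS-ID item list, since section 5.3 announces nine TAPS-2 categories but names eight.
3. Leave medication items out of any compared score. Include opiates and other substances only where illicit use can be separated from medication; otherwise report the comparison with and without them.
4. Report medication items descriptively within the section 6.7 overview, naming them there.
5. State that the study does not establish criterion validity of the medication category in patients with intellectual disability.

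The cost is mainly wording, plus a check of the final items. Step 2 may take more work: section 5.3 describes a broad interview and gives no scoring, so whether outcomes per domain can be drawn from it cannot be checked here. The downside is that the sponsor could not claim the whole TAPS-ID as validated. If that claim is wanted, a separate reference for medication misuse is needed, with new data, added patient burden and changed consent.

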2. OBJECTIVES

There are two objectives:

1. Validating and implementing the TAPS in patients with a severe mental disorder and problematic substance use.
2. Developing, validating and implementing the TAPS-ID in patients with a mental disorder, intellectual disability (ID) and problematic substance use.

3. STUDY DESIGN

This is a descriptive study based on routinely collected data. The FACT teams that participate in the study work according to a care program in which screening and assessment are part of the standard care. This implies that since 2016, screening has been carried out at the start of treatment for: PTSD, a mild intellectual disability, addiction problems. The current screening for addiction problems is too limited and lacks a follow-up step in the form of structured assessment. In addition, at the start of treatment and annually in preparation of the treatment plan, the level of complaints is assessed by the care provider involved and the phase of recovery and the patient's quality of life are assessed. We want to use this data from patients in whom there is no suspicion of mild intellectual disability in anonymised form. In the research into the validity of the TAPS, we want to measure whether there is a relationship between the existence of problem substance use and a poorer treatment outcome (less decrease in complaints), and a reduced quality of life.

The TAPS has already been included as a replacement for the previously used screener for addiction problems by the various substantive advisory bodies that deal with the content and improvement of the care of the GGZ Oost Brabant.

In order to investigate the concurrent validity of the TAPS, a group of at least 40 patients will be asked permission to administer some parts of the MATE in addition to the TAPS.

The TAPS is too difficult for patients with intellectual disabilities. We therefore made adjustments to the translated TAPS (see below). The adjusted version for patients with ID is called the TAPS-ID. The validity of the TAPS-ID is examined by the comparison of the TAPS-ID and the SumID-Q (an instrument specially developed to map addiction problems in patients with MID). This will be carried out in a special department within secondary healthcare for patients with a combination of a severe mental disorder and intellectual disability (LVB-P) and in a healthcare setting for people with intellectual disabilities with minimal or light mental disorders (ORO). The SumID-Q is part of standard care for both departments. Trained employees who administer the SumID-Q also take the TAPS-ID.

We would like to analyze the results of these measurements retrospectively over a period of at least 6 months by placing them anonymously and not traceable to individual persons in an SPSS database. We would also like to add some very global background data to this, namely: sex, age in years and the main psychiatric diagnosis. This data will be added to the database without name or other personally identifiable information by a secretary who is affiliated with the research line and who has access to this data in that regard. For this

reason, this secretary also has temporary access to the secured data from the electronic patient file.

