The course of the complaints is mapped out annually using the HoNOS (Health of the Nation Scale). This is an observation list that is completed by the practitioner. The outcome of the HoNOS reflects the mental and social functioning of a client in mental health care at a given moment. The HoNOS can be completed at several moments before, during or after a treatment, so that the change in complaints is mapped out. The aim of the HoNOS is therefore to evaluate the treatment or supervision. The score for the 12 items that make up the instrument always ranges from 0 (no problem) to 4 (very serious problem). These are issues that have occurred in the past two weeks. Psychometric properties of the HoNOS are satisfactory to good (Mulder et al., 2004).

MANSA:

The quality of life, as experienced by the patient, is mapped with the MANSA: the Manchester abbreviated quality of life measure (Van Nieuwenhuizen, Schene & Koeter, 2000), the 16 item version. The MANSA is a multidimensional questionnaire

designed to assess quality of life. The closed questions refer to job satisfaction, housing, general health and social relationships.

MATE:

MATE is the Dutch abbreviation of “Measurement of Addiction for Triage and Evaluation”. It is an instrument, developed in Europe to determine patient characteristics for the indication of care for people with addiction problems on a valid and reliable way. The MATE has ten modules (eight interview modules and two self-report questionnaires) which take about one hour to assess totally. These modules are: 1. substance use, 2. substance abuse and dependence, 3. craving, 4. depression, anxiety and stress, 5. psychotic symptoms, suicidality and current psychiatric treatment, 6. personality disorders, 7. physical complaints and symptoms 8. personal and societal functioning, 9. environmental factors influencing recovery, and 10. history of substance abuse treatment. The MATE comprises a set of existing, well-developed and widely accepted instruments to investigate the ten module-themes: for example the CIDI (Composite International Diagnostic Interview) to investigate ICD criteria, the DASS (Depression Anxiety Stress Scales) to investigate depression and anxiety, and the SAPA (Standard Assessment of Personality Abbreviated scale) to investigate personality disorders.

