6. SAFETY REPORTING

6.1 Temporary halt for reasons of subject safety

This is not applicable because it is a retrospective observational study with one moment of data collection.

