6.4 Follow-up of adverse events

N.a.

6.5 [Data Safety Monitoring Board (DSMB) / Safety Committee]

The data were gathered in routine treatment procedures. For the purpose of the study, after merging several sources in full database case numbers were anonymized in a way no cases could be traced back. Fully anonymized and corrected data were handed over to the research team. The authors assert that all procedures contributing to this work comply with the ethical standards of the relevant national and institutional committees on human experimentation and with the Helsinki Declaration of 1975, as revised in 2008. The Ethical Commission of the Radboud University, Social Sciences, the Netherlands, reviewed the procedure used in this study and decided that, because no actions or behaviours are imposed on the participants, there was no need for further ethical review.

STATISTICAL ANALYSIS

This study will not test any intervention. It will focus on the level of agreement between patients responses on the newly used instrument for screening and brief assessment of addiction problems (TAPS/TAPS-ID) and the golden standard (MATE / SumID-Q).

Research goal 1:

- With regard to the reliability of the TAPS, the internal consistency is determined (Cronbach's alpha and item-total correlation). To determine the convergent validity, first the correlation is determined between the outcome of the TAPS (indications of problematic use) and the outcome of the severity of the addiction on the MATE (degree of severity).
- To investigate the influence of addiction problems on treatment outcomes and quality of life, the correlation with the outcomes of the Honos and Mansa is calculated. The hypothesis is that a higher score on the TAPS correlates with a higher score on the Honos and a lower score on the Mansa.
- The optimal cut-off point of the TAPS is determined by means of ROC analyses.

Research goal 2:

- For the development of the TAPS-ID, the feasibility (by the interviewers) and feasibility (with the target group) will first be estimated on the basis of a few interviews with the interviewers involved.
- With regard to the reliability of the TAPS, the internal consistency is determined (Cronbach's alpha and item-total correlation). To determine the convergent validity, the correlation is determined between the outcome of the TAPS and the outcome of the SumID-Q.

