6.6 Primary study parameter(s)

Statistical analysis will examine agreement between different measures of substance use (sensitivity, specificity and AUC value) to evaluate the level of classification accuracy for each items or candidate combination of items.

This study will not include follow up assessments. We expect a number of patients who don't want the assessment at all or don't want to sign informed consent. The extent of missing data will be analyzed and explore differences in missing data by age, gender, and diagnosis.

On objective 1 the primary study parameters are TAPS and MATE outcomes. The total TAPS-score is used as

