6.7 Secondary study parameter(s)

The analysis of size and content of addiction problems will be done by an overview of descriptive statistics of the whole patient population, sorted by different substances being used.

For objective 1 the correlation with quality of life (MANSA) and amount of mental complains and social functioning (HoNOS) is also calculated for the divergent validity.

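### The secondary question about less decrease in complaints is paired only with a score-level HoNOS correlation, which cannot answer a question about change

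*Combined protocol and SAP*

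**What the plan says.** - **Question.** Section 3 wants to know "whether there is a relationship between the existence of problem substance use and a poorer treatment outcome (less decrease in complaints"), and whether quality of life is reduced. The first part concerns change; the second concerns level.
- **Analysis.** The method stands under Statistical analysis, Research goal 1: "To investigate the influence of addiction problems on treatment outcomes and quality of life, the correlation with the outcomes of the Honos and Mansa". Nothing more is specified about how this correlation is formed.
- **Expected direction.** The same bullet predicts the sign of both associations, in terms of score level: "a higher score on the TAPS correlates with a higher score on the Honos and a lower score on the Mansa".
- **Label.** Section 6.7 says the same correlation "is also calculated for the divergent validity".
- **Available scores.** Section 3 states that "at the start of treatment and annually in preparation of the treatment plan, the level of complaints is assessed". Section 5.3 adds: "The HoNOS can be completed at several moments before, during or after a treatment, so that the change in complaints is mapped out".
- **Timing.** Section 6.6 says: "This study will not include follow up assessments". Sections 6.1 and 6.2, on safety, say that "it is a retrospective observational study with one moment of data collection". Section 3 also gives a retrospective window with a minimum of 6 months, which is shorter than the annual HoNOS interval.
- **Status.** Section 5.1.2 lists quality of life and mental complaints as secondary.

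**The concern.** The question and the analysis do not match. A decrease in complaints needs two scores per patient, or one later score adjusted for the first. The plan names neither, and it does not say which HoNOS (first, annual or latest) enters the correlation. Followed as written, the study could report an association between score levels as evidence about treatment outcome. That evidence would be silent on whether patients with substance use problems improve less.

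There is a smaller issue with the label. Divergent validity is normally supported by a weak or absent correlation with a different construct, whereas the hypothesis predicts a directional one. No expected size or upper limit is given, so no result could count for or against the label.

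**Working it through.** **No plan figure to reproduce for this analysis.** The documents give no expected correlation, alpha or power for HoNOS or MANSA. The one related calculation, in section 4.4, does reproduce: 100 new patients per year × 2.5 years × (1 - 0.40) = 150.

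**Can a level correlation settle the change question?** Let r0 be the correlation of TAPS with intake HoNOS, r1 the correlation of TAPS with 12-month HoNOS, and s the correlation between the two HoNOS scores. All values are assumed. The baseline-adjusted partial correlation is

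(r1 - r0·s) / √[(1 - r0²)(1 - s²)].

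With r0 = 0.30 and s = 0.60, the numerator is r1 - 0.18 and the denominator is √(0.91 × 0.64) = 0.763.

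| r1 | partial r | meaning |
|---|---|---|
| 0.10 | -0.10 | more decrease with higher TAPS |
| 0.18 | 0.00 | no difference |
| 0.30 | 0.16 | less decrease |
| 0.40 | 0.29 | less decrease |

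The intake correlation is 0.30 in every row. Sensitivity to s: the zero point r0·s moves from 0.12 (s = 0.40) to 0.24 (s = 0.80). At r1 = 0.18 the partial runs from +0.07 to -0.10.

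Raw change gives the same picture. With equal SDs, the correlation of TAPS with decrease is (r0 - r1)/√(2 - 2s). For r0 = 0.30 and r1 = 0.20, 0.30 or 0.40, it is +0.10, 0.00 or -0.10 at s = 0.50, and +0.13, 0.00 or -0.13 at s = 0.70. Here positive means more decrease.

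**Precision if the analysis stays cross-sectional.** Fisher-z 95% intervals for an observed r of 0.30 are -0.01 to 0.56 at n = 40 and 0.11 to 0.47 at n = 100.

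**How many patients would have a 12-month score?** This assumes uniform accrual, complete routine scores and no dropout.

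- Minimum of 40 participants over 2.5 years: 40 × 1.5/2.5 = 24.
- Every eligible patient consents, so 150/2.5 = 60 per year, with data extracted when the stop at 100 is reached: 100/60 = 1.67 years, and (1.67 - 1) × 60 = 40.
- Same accrual, with data extracted at 2.5 years: 1.5 × 60 = 90.

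Approximate power for the adjusted association (Fisher z, two-sided 0.05, one covariate, SE = 1/√(n - 4)):

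| n | partial 0.30 | partial 0.16 |
|---|---|---|
| 24 | 0.28 | 0.11 |
| 40 | 0.46 | 0.16 |
| 90 | 0.82 | 0.31 |

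The second column uses the unrounded partial of 0.157 from the table above.

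**The case against.** The strongest reply is that the working plan is a level correlation and only loose wording suggests more. Section 3 calls the study descriptive and asks about a relationship, the objectives in section 2 contain no treatment-outcome aim, and the hypothesis is on score level. This stands as a limit on the consequence: the reference to influence does not show that a causal claim is planned. It does not remove the mismatch, because section 3 names less decrease explicitly and no analysis addresses it.

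A reader might infer from sections 6.1, 6.2 and 6.6 that only one HoNOS per patient exists, so that change could never be studied. The documents do not support that. Those statements may mean only that the study adds no visits. Section 3 states the wish to use routine data directly after describing the start and annual assessments, and the 6-month window is a minimum. Whether annual scores are meant to be used is unclear, not excluded.

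A reader might also infer that the divergent-validity label contradicts the hypothesis or makes it untestable. It does neither. The directional hypothesis can be tested as written, and a directional correlation weaker than the TAPS–MATE correlation can fit the label. What is missing is a size criterion.

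Finally, the correlations used above are assumed. They show that the change question is undetermined, not what the study will find.

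**Conclusion.** The point holds for the secondary endpoints and should be fixed. As written, a question about change would be answered with a level correlation that is compatible with more, equal or less improvement: partial correlations from -0.10 to 0.29 under the assumed r0 = 0.30 and s = 0.60. That a level correlation leaves the direction of change open does not depend on those particular values.

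It would go too far to infer that the validation itself is compromised. The primary TAPS–MATE comparison is unaffected, and a level correlation suits the quality-of-life question once the MANSA time point is named.

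**What to change.** 1. State first whether routine annual scores will be used. Name the HoNOS and MANSA time point and score, and reconcile sections 3, 5.3, 6.1, 6.2 and 6.6 with that statement.
2. If annual scores will not be used, reword section 3 and Research goal 1 as a cross-sectional association, for example the correlation of the TAPS score with HoNOS and MANSA scores at intake, with a 95% confidence interval. Drop the references to treatment outcome, less decrease and influence.
3. If they will be used, answer the change question with a regression of 12-month HoNOS on intake TAPS, with intake HoNOS as covariate, reported as exploratory. The scores must be merged before the irreversible anonymisation described in section 6.5.
4. In either case, confirm that use of HoNOS and MANSA is covered by consent or by the ethics decision. The consent described in section 5.3 for objective 1 covers TAPS, MATE and background data, and names neither scale at any time point.
5. In section 6.7, either call the correlation hypothesised construct validity, or keep the divergent label and state an expected size, for example weaker than the TAPS–MATE correlation.

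The cost is small. The cross-sectional route needs rewording and the permission check, but no new data. The regression would be imprecise: about 24 patients at the minimum participation, or 40 to 90 with full consent, before dropout. Its power is at best 0.82 for an assumed partial correlation of 0.30 and 0.31 for 0.16.
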